### 1.4.2 *Number of subjects*

Despite the corrective actions conducted in the patients' recruitment process, the final number of subjects expected to be included in the study is around 100.

With a sample of 100 subjects, a precision between  $\pm 4.9\%$  and 39.2% is obtained for a standard deviation between  $\frac{1}{4}$  and 2 times the mean.

**Table 2: Precision of a 95% CI for a continuous variable, taking into account the standard deviation and a sample size of 100 patients, according to the normal distribution of the mean**

Sample size (n)	Standard Deviation (SD as % of the mean)					
	1/4	2/4	3/4	1	1,5	2
100	4,9%	9,8%	14,7%	19,6%	29,4%	39,2%

$\pm 1,96 \cdot SD / \sqrt{n}$ , with SD the standard deviation and n the sample size.

All the analyses will be performed as initially planned, except when the number of patients in a subgroup of interest is below 5.

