#### 4. GENERAL STATISTICAL APPROACH

All statistical analyses will be descriptive and will provide description of the data along with 95% 2-sided CIs.

The quantitative variables are summarized using the following parameters:

- Number of non-missing data,
- Number of missing data,
- Mean,
- Standard deviation,
- Median and first & third quartiles
- Minimum,
- Maximum.

The qualitative variables are summarized using the following parameters:

- Number of non-missing data,
- Number of missing data,
- Counts and percentages

Missing data or unknown responses are not counted in the percentages, but numbers of missing data are presented in the results tables.

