### 5.1.2.2 EQ-5D-5L

Each item of the EQ-5D-5L is considered for analysis.

A total of 3125 ( $5^5$ ) possible health states can be defined through the 5 levels of answers of the 5 dimensions of the EQ-5D-5L.

A single index value, country-specific (France for this study), is used for valorizing each health state.

Since, at time of this SAP writing, no indexes exist for the EQ-5D-5L for France, the crosswalk value set from the EQ-5D-3L computed on a study on 3691 patients with different diseases and from different countries will be used, as recommended by the EuroQol group.

The change of quantitative criteria from Inclusion to phone interviews at M1, M3 (M6 and M9 for PHN cohort) are assessed as well: value at phone interview – value at inclusion.

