#### 5.2.2.2.2 Patient reported outcomes

PRO variables (see section 5.1.2) will be analyzed in a descriptive way according to the general statistical approach described in section 4, by time frame (inclusion, 1 month, 3 months, and for PHN: 6 months and 9 months).

Analysis of evolutions from inclusion will also be conducted by time frame, by use of the Wilcoxon signed rank test for quantitative criteria and by use of the Mc Nemar's test for binary criteria in the HZ cohort.

Spaghetti plots will be produced for describing the evolutions in the PHN cohort.

In addition, for the analysis of the EQ-5D-5L indexes, the reference value of the index for France for EQ5D-3L indexes (Chevalier J, 2013) is used for assessing the average loss in quality of life at inclusion and by time frame.

As a sensitivity analysis, means and 95%CI of the means of the EQ-5D-5L index will also be estimated by a generalized linear model, with Gamma distribution and log as link function.

Consistency between PRO measurements will be assessed by scatter plots crossing the individual items of the ZBPI with the individual items of the EQ-5D-5L, at baseline, at 1 month and at 3 months, for the HZ cohort.

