### 5.2.2.3 Costs analysis

The costs assessment will be made for patients with both interviews conducted at 1 month and at 3 months. The costs assessments of the PHN cohort at 6 and 9 months will be made for patients who have also both interviews conducted at 6 and 9 months.

For both approaches (societal and payer), direct medical costs and indirect costs will be summed from inclusion up to 3 months for the global HZ cohort. For the PHN cohort, costs will be summed from inclusion up to 6 months and from inclusion up to 9 months. For the PHN cohort, costs will also be summed from inclusion up to 3 months, for comparison to the rest of the global HZ cohort.

Means and 95%CI of the means will be estimated by a generalized linear model, with Gamma distribution and log as link function.

Histograms of the costs will be produced for the HZ cohort. Values of the costs obtained in the PHN cohort will be plotted patient by patient.

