### 6.1 Missing data

Missing data will not be replaced.

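### The Gamma/log sensitivity model for the EQ-5D-5L index adds nothing on the mean, puts an unsuitable shape behind its interval, and cannot use index values at or below 0

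*SAP*

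**What the plan says.** The main analysis of the index is descriptive. Section 5.2.2.2.2 states: "PRO variables (see section 5.1.2) will be analyzed in a descriptive way according to the general statistical approach described in section 4". Section 4 lists the mean, standard deviation, quartiles, minimum, maximum and missing counts, and adds: "All statistical analyses will be descriptive and will provide description of the data along with 95% 2-sided CIs".

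Section 5.2.2.2.2 then adds the sensitivity analysis: "means of the EQ-5D-5L index will also be estimated by a generalized linear model, with Gamma distribution", with a log link. It names no covariate, no transformation of the index (such as 1 minus the index), no dispersion estimate and no rule for values at or below 0. Apart from the variable, the specification is that of section 5.2.2.3 for costs: "Means and 95%CI of the means will be estimated by a generalized linear model, with Gamma distribution and log as link function".

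On the index itself, section 5.1.2.2 says: "A single index value, country-specific (France for this study), is used for valorizing each health state". It takes the French crosswalk set but gives no range, floor or expected distribution. Section 6.1 adds only: "Missing data will not be replaced". Section 1.4.2 gives the size of the study: "the final number of subjects expected to be included in the study is around 100".

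**The concern.** A Gamma model is a natural choice for costs, which are right-skewed and have no upper limit. A preference index runs the other way: its best state is the top of the scale, and ill patients lie below it. Two consequences follow.

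- If all values are positive, the model cannot give a mean different from the main analysis. Only the interval can change, and it changes through a variance assumption made for another kind of variable.
- If any value is at or below 0, the patients in the worst health drop out of the sensitivity analysis and its mean rises.

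Quality of life is a secondary objective (section 1.1), and section 5.2.2.2.2 uses the index to express the average loss against a French reference value. A mean that is too high understates a loss computed from it by the same amount.

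**Working it through.** **The plan's own figure.** The only precision figure in the SAP that applies to utilities at the revised sample size is Table 2 (section 1.4.2): half-width = 1.96 × SD/√n as a percentage of the mean. For n = 100 and SD = 1/4 of the mean, 1.96 × 0.25/10 = 4.9%. For SD = 2 times the mean, 1.96 × 2/10 = 39.2%. Both reproduce. The SAP gives no figure for the sensitivity analysis.

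**Step 1: all values positive.** For a Gamma model with common mean μ and log link, the score equation is Σ(y − μ)/μ = 0, so the estimate of μ is the sample mean. This is algebra and holds whatever the skew. On a simulated left-skewed index (n = 100, skew −0.84), the arithmetic mean and the Gamma/log mean were both 0.8387. With one factor, such as gender or the two age classes of section 5.2.2.2, the same equation applies within each level and returns the group means.

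**Step 2: the interval.** With m the mean of the values used, n their number and CV their SD/m, the 95% interval is
- Pearson dispersion: m × exp(±1.96 × CV/√n)
- maximum-likelihood (ML) shape k: m × exp(±1.96/√(k n))

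The SAP does not say which applies.

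**Step 3: values at or below 0.** The Gamma log-likelihood contains a term in log y, so it is undefined for such values. I assume that they are dropped. If a share q is dropped, the mean rises by q × (m₊ − m₀), where m₊ and m₀ are the means of the positive and non-positive values. With assumed m₊ = 0.70 and m₀ from −0.05 to −0.20:
- q = 2%: 0.02 × 0.75 to 0.02 × 0.90 = 0.015 to 0.018
- q = 5%: 0.05 × 0.75 to 0.05 × 0.90 = 0.037 to 0.045
- q = 10%: 0.10 × 0.75 to 0.10 × 0.90 = 0.075 to 0.090
- one patient in a PHN cohort of 16 (16% at M3 from section 1.3.1, applied to about 100): 0.0625 × 0.75 to 0.0625 × 0.90 = 0.047 to 0.056

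**Step 4: simulation.** Assumed index = 1 − 1.5 × Beta(0.9, b), which lies on (−0.5, 1) with a left tail. The mean disutility is 0.2, 0.3 or 0.4, which gives b = 5.85, 3.60 or 2.475. There were 3000 replicates with n = 100. The t interval uses all values; the Gamma model uses positive values only.

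| True mean | Share ≤ 0 | Mean of usable values | Coverage, Gamma ML | Coverage, Gamma Pearson | Coverage, t |
|---|---|---|---|---|---|
| 0.80 | 0.1% | 0.801 | 97% | 94% | about 95% |
| 0.70 | 1.6% | 0.713–0.714 | 95% | 89% | about 95% |
| 0.60 | 5.7% | 0.645 | 78% | 59% | about 95% |

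At true mean 0.80 the ML-based interval has width 0.085 against 0.072 for the t interval, which is 18% wider (0.085/0.072 = 1.18). In 88% of those samples no value is at or below 0, so the two means are identical. A percentile bootstrap on all values covers 94–95% in all three scenarios.

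**The case against.** The strongest reply is that the harmful case rests on facts outside the SAP. Section 5.1.2.2 gives no ceiling value, skew or negative values, and the floor of −0.5 and the Beta shape in the simulation are my choices. This stands: the upward bias is conditional. Even under these assumptions the ML-based interval has nominal or slightly conservative coverage in two of the three scenarios. The Pearson version falls short in one of those two (89%).

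A reader might infer that the check gives false reassurance about robustness. The SAP does not support that. It plans a mean with its interval, the interval does change, and no conclusion about robustness is drawn from agreement of the means.

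A reader might also infer that the trial's quality-of-life results will be overstated. That does not follow either. The main descriptive analysis uses all observed values, a value at or below 0 would show in the reported minimum, and a shifted sensitivity mean would stand beside the unaffected one. No cost result under the primary objective depends on this model.

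Finally, a bootstrap also leaves the point estimate at the arithmetic mean. The fact that the Gamma mean cannot differ is therefore no argument for the bootstrap. What favours it is that it keeps every observed value and assumes no Gamma shape.

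**Conclusion.** The point holds, at low severity. Certain from the model as written: with no covariate or one factor, and all values positive, the analysis adds no information on the mean and alters only the interval, through a shape suited to costs. Conditional on the value set giving values at or below 0, which the SAP neither states nor excludes: those patients are lost and the sensitivity mean is too high. Under the assumed distribution with n = 100, the bias runs from negligible at a true mean of 0.80 to about +0.045 at 0.60, where coverage falls to 78% (ML) or 59% (Pearson). In a PHN cohort of about 16, a single such patient would move the mean by about 0.05. The main mean is unaffected, and this is one sensitivity analysis under a secondary objective.

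**What to change.** In section 5.2.2.2.2, replace the Gamma/log model for the EQ-5D-5L index by a bootstrap 95% interval (percentile or BCa) for the mean index and for the mean loss against the reference value, using all observed values including any at or below 0. Describe it as a check of the interval against non-normality at small sample size, not as an independent check of the mean. The Gamma/log model for costs in section 5.2.2.3 is not touched by this point. The cost is a change of SAP wording and a few lines of SAS; no new data are needed.

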#### 5.2.2.2.3 Health care resources

Health care resources variables (see section 5.1.3) will be analyzed in a descriptive way according to the general statistical approach described in section 4, by time frame (inclusion, 1 month, 3 months, and for PHN: 6 months and 9 months) and for the global study period.

For medications, number and percentages of patients with at least one medication by anatomical and therapeutical category (patients are counted once if many medications fall in the same category) will be presented by time frame and on the whole period.

The cumulative number of days of sick leave, the cumulative number of visits to a general practitioner, the cumulative number of visits to a specialist (globally and by specialty), the cumulative number of visits to emergency room and the cumulative number of days of hospitalization, will be presented by time frame and on the whole period.

The cumulative number of days of sick leave will also be presented by time frame and on the whole period for patients working full time or part time.

Spaghetti plots will be produced for describing the quantitative health care resources data in the PHN cohort.

### 5.2.2.3 Costs analysis

The costs assessment will be made for patients with both interviews conducted at 1 month and at 3 months. The costs assessments of the PHN cohort at 6 and 9 months will be made for patients who have also both interviews conducted at 6 and 9 months.

For both approaches (societal and payer), direct medical costs and indirect costs will be summed from inclusion up to 3 months for the global HZ cohort. For the PHN cohort, costs will be summed from inclusion up to 6 months and from inclusion up to 9 months. For the PHN cohort, costs will also be summed from inclusion up to 3 months, for comparison to the rest of the global HZ cohort.

Means and 95%CI of the means will be estimated by a generalized linear model, with Gamma distribution and log as link function.

Histograms of the costs will be produced for the HZ cohort. Values of the costs obtained in the PHN cohort will be plotted patient by patient.

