### 1.3 Determination of sample size

#### 1.3.1 Subjects

The study was initially designed to include 250 cases of HZ with 40 cases of PHN expected (hypothesis of 16% of PHN at M3).

For quantitative variables, such as costs and utilities, the precision is a function of the variability of the variable. With a sample of 250 subjects, a precision between  $\pm 3.1\%$  and 24.8% is obtained for a standard deviation between  $\frac{1}{4}$  and 2 times the mean. With 40 subjects and still a standard deviation between  $\frac{1}{4}$  and 2 times the mean, a precision of the mean between  $\pm 7.7\%$  and 62.0% is obtained.

**Table 1: Precision of a 95% CI for a continuous variable, taking into account the standard deviation and sample size, according to the normal distribution of the mean**

Sample size (n)	Standard Deviation (SD as % of the mean)					
	1/4	2/4	3/4	1	1,5	2
250	3,1%	6,2%	9,3%	12,4%	18,6%	24,8%
40	7,7%	15,5%	23,2%	31,0%	46,5%	62,0%

$\pm 1,96 \times SD / \sqrt{n}$ , with SD the standard deviation and n the sample size.

GlaxoSmithKline

POSTHER

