### 5.1.4 Costs assessments

The costs are evaluated by time frame:

- At inclusion
- Cumulatively up to 1 month
- Cumulatively up to 3 months
- Cumulatively from 1 to 3 months
- Cumulatively up to 6 months for PHN cohort
- Cumulatively from 3 to 6 months for PHN cohort

- Cumulatively up to 9 months for PHN cohort
- Cumulatively from 6 to 9 months for PHN cohort The type of costs evaluated are:
- Direct medical costs: hospital stays, emergency room visits, medical visits, medications - Indirect costs: patient sick leave

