### 6.2 Windows for time points

Phone interviews should be conducted at 1 month +/- 3 days, at 3 months +/- 1 week (and for PHN cohort at 6 months +/- 1 week and 9 months +/- 1 week).

Automatic emails and calendar were sent to the nurses in charge of phone interviews for optimal management.

Interviews conducted > 30 days before or after the theoretical date will be considered as missing.

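### The interview-completeness rules for costs drop early-frame costs that are fully observed, and the SAP has no check for selective dropout in any cost total

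*SAP*

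**What the plan says.** Section 5.2.2.3 sets two entry rules for the cost analysis. The general one is: "The costs assessment will be made for patients with both interviews conducted at 1 month and at 3 months". The second applies to the PHN cohort at 6 and 9 months, whose costs are assessed for "patients who have also both interviews conducted at 6 and 9 months".

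Several of the planned outputs end before the last interview that these rules demand. Section 5.1.4 lists costs at inclusion, then "Cumulatively up to 1 month", and for the PHN cohort a 3-6 month frame and a total up to 6 months. Section 5.2.2.3 repeats the 6-month total as an output of its own: "For the PHN cohort, costs will be summed from inclusion up to 6 months and from inclusion up to 9 months".

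Two conventions bear on this. Section 6.1 states: "Missing data will not be replaced". Section 6.2 adds: "Interviews conducted > 30 days before or after the theoretical date will be considered as missing". An M9 interview held too far off schedule therefore has the same effect as no M9 interview.

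**The concern.** A cost up to a given time needs only the data collected up to that time. The inclusion cost needs no interview at all: the visit is valued from the investigator's specialty (section 5.1.4.1.2), and medicines bought before inclusion are recorded by the physician (section 3.3.1). The 0-1 month cost needs M1. The PHN 0-6 month cost needs M1, M3 and M6. Under section 5.2.2.3 these costs are nevertheless set aside when a later interview is missing, although that interview contributes nothing to them.

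Two things are at stake. Precision is lost, and the PHN cohort has the least to spare; section 5.2.2.2 itself expects it to be very small. In addition, costs are the primary objective (section 1.1), and all cost estimates are complete-case. The SAP plans no imputation, weighting, available-data analysis or comparison of completers with non-completers for costs. Its only sensitivity analysis of a mean concerns the EQ-5D-5L index (section 5.2.2.2.2). If patients who stop answering differ in recovery or severity, nothing planned for costs would show it.

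**Working it through.** **Inputs from the SAP**
- Original plan (section 1.3.1): 250 HZ cases with "40 cases of PHN expected (hypothesis of 16% of PHN at M3").
- Revised size (section 1.4.2): "the final number of subjects expected to be included in the study is around 100".
- PHN status is defined by the M3 interview (sections 2.1 and 2.2), so M3 is present for every PHN patient.
- Relative half-width of a 95% CI (Tables 1 and 2): 1.96 × (SD/mean) / √n.

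**Assumption, not in the SAP**
- A fraction q of 10% or 20% is missing at each interview, independently of the others. The SAP gives no attrition rate.

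**Step 1: reproduce the SAP's figures.** 0.16 × 250 = 40 PHN cases, as stated. At SD = mean the formula gives 12.4% for n = 250, 31.0% for n = 40 and 19.6% for n = 100. All cells of Tables 1 and 2 reproduce.

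**Step 2: size of the PHN cohort now.** 0.16 × 100 = 16, with a binomial 95% range of about 9 to 23. The SAP has no precision row for this size. At SD = mean it is 1.96/√16 = 49.0%, before any loss.

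**Step 3: who is dropped without need**

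| Frame | Interviews needed | Interviews the SAP requires |
|---|---|---|
| Inclusion | none | M1, M3 |
| 0-1 month | M1 | M1, M3 |
| 0-3 months | M1, M3 | M1, M3 |
| PHN 3-6 months | M6 | M1, M3, M6, M9 |
| PHN 0-6 months | M1, M3, M6 | M1, M3, M6, M9 |
| PHN 0-9 months | M1, M3, M6, M9 | M1, M3, M6, M9 |

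The 0-3 and 0-9 month rows match, so nothing is discarded needlessly there.

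**Step 4: usable patients**
- HZ 0-1 month, needed: 100(1−q) = 90 or 80. SAP rule: 100(1−q)² = 81 or 64.
- PHN 0-6 months, needed: 16(1−q)² = 13.0 or 10.2 (losses at M1 and M6 only). SAP rule: 16(1−q)³ = 11.7 or 8.2.

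**Step 5: effect on the interval.** In both cases the SAP rule multiplies n by (1−q), so the interval widens by 1/√(1−q): 1.054 at 10% and 1.118 at 20%. For the PHN 0-6 month cost at SD = mean, the half-width goes from 1.96/√12.96 = 54% to 1.96/√11.66 = 57% (q = 10%), or from 1.96/√10.24 = 61% to 1.96/√8.19 = 68% (q = 20%). The planned gamma model with log link gives a somewhat different interval, but its width on the log scale also varies as 1/√n for a given dispersion.

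**Step 6: dependence on the assumption.** The ratio in step 5 depends only on the fraction missing the later interview among patients who have the earlier ones. If only M9 is ever missed, the PHN 0-6 month n is 16 when M9 is not required, against 14.4 or 12.8 under the rule, and the ratio is unchanged. If the same patients tend to miss several interviews, that fraction is below q and the needless loss is smaller.

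**The case against.** The strongest defence is comparability. On one common set of patients the frames add up, and the step from 0-6 to 0-9 months shows cost growth alone. With frame-specific sets it also reflects a change of patients. That is a legitimate reason, and it stands as a reason to keep the common set in the report. It does not settle the matter, because the SAP does not give this reason and does not hold fully to one set: PHN 0-3 month costs need M1 and M3 only, so PHN denominators already change between frames.

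The loss is also small in patients: about 1.3 (q = 10%) or 2.0 (q = 20%) PHN patients, in an estimate that is imprecise either way. Those counts rest on an assumed rate. Excluded patients are not invisible either. Resource use is described by time frame without a completeness rule (section 5.2.2.2.3), missing counts are reported (section 4), and every PHN patient has an individual profile (section 5.2.2.2). All of this limits the size of the point, but none of it checks the cost estimates.

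Three stronger readings are tempting and are not supported.
- A reader might infer that every cost rests on patients who completed all interviews. It does not: a PHN patient who misses M6 or M9 stays in the 0-3 month cost.
- A reader might infer that the main totals needlessly lose patients. The 0-3 month HZ and 0-9 month PHN totals require exactly the interviews they need.
- A reader might infer that the primary cost is biased. The SAP has no information on who stops answering or why. What can be said is that bias could not be detected. Changing the inclusion rule alone would not cure it, since frame-specific sets are still complete-case.

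**Conclusion.** The concern holds in a limited form. Section 5.2.2.3 drops fully observed inclusion and 0-1 month costs for patients without M3, and fully observed 0-6 and 3-6 month costs for PHN patients without M9. With 10-20% missing per interview, the 0-1 and 0-6 month intervals are about 5-12% wider than they need be. This rests on an assumed, independent missing rate and on a PHN cohort of about 16, a figure derived from the SAP's 16% and its revised total and not stated in it.

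For the 0-3 month HZ and 0-9 month PHN totals the point is a different one: they are complete-case estimates of the primary objective with no planned check for selective dropout. Neither part invalidates the analysis. Both are worth correcting because the data are already collected.

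**What to change.** - **Primary cost tables.** For each frame in section 5.1.4, include every patient with the interviews that cover it. Inclusion: none. 0-1 month: M1. 0-3 months: M1 and M3. 0-6 months: M1, M3 and M6. 0-9 months: all four. Interval frames need the interview that records that interval. Show n for every frame.
- **Secondary table.** Keep the all-interview set, so that frames remain additive on the same patients.
- **Sensitivity check on the 0-3 and 0-9 month totals.** Add up the interval means, each taken from all patients with that interview, with a bootstrap CI that resamples patients. In the PHN cohort, read this interval cautiously because n is small.
- **Completers and non-completers.** Compare their inclusion characteristics.
- **Actual counts.** Report how many patients miss each interview, including those set to missing under section 6.2. These counts replace the assumed 10-20%.

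The cost is some SAP wording and a few extra tables, with no new data. The downside is that denominators differ between frames, so changes from one frame to the next should be read from the secondary table.

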### 1.1 Objectives

The primary objective is to evaluate Herpes Zoster (HZ)-related and Post Herpetic Neuralgia (PHN)-related direct medical costs and indirect costs during a 9 months period (overall, by gender and classes of age) among people  $\geq 50$  years old in France.

Secondary objectives are:

- To describe HZ and PHN pain severity during a 9 months period (overall and by classes of age)
- To evaluate the impact of HZ and PHN on the quality of life of patients during a 9 months period (overall by gender and by classes of age)

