Acupuncturist	23.00	70% - 1€	https://www.ameli.fr/l-assurance-maladie/statistiques-et-publications/donneesstatistiques/professionnels-de-santeliberaux/honoraires/honoraires-taux-etmoyens.phpsource - 2014

The cost for radiologists, healers, magnetizers will not be valorized.

The cost of the inclusion visit is evaluated according to the specialty of the investigator: general practitioner, dermatologist, ophthalmologist.

The cost of each medical visit recorded through phone interviews is evaluated according to the specialty visited.

The medical visit costs for one patient are the sum of all the costs of the visits made by the patient by time frame.

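### The Gamma/log model for cost means has no stated scope and no rule for zeros, so it does not fit indirect cost or the interval costs, which can be 0

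*SAP*

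**What the plan says.** The primary objective in SAP section 1.1 covers "direct medical costs and indirect costs during a 9 months period (overall, by gender and classes of age", so direct and indirect costs are both named. Section 5.1.4 defines the second in one line, "Indirect costs: patient sick leave", and section 5.1.4.2 values it as days missed times a daily allowance of 32.74 euro. Section 5.1.4 also lists interval time frames such as "Cumulatively from 1 to 3 months", with 3-6 and 6-9 months for the PHN cohort.

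Section 5.2.2.3 fixes the population: "The costs assessment will be made for patients with both interviews conducted at 1 month and at 3 months". PHN costs at 6 and 9 months additionally require both later interviews. The section then describes sums of direct and indirect costs from inclusion, and follows with the model: "Means and 95%CI of the means will be estimated by a generalized linear model, with Gamma distribution and log as link function". It gives no list of cost variables and no rule for zeros.

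Two other passages bear on the point. Section 4 promises "All statistical analyses will be descriptive and will provide description of the data along with 95% 2-sided CIs" without saying how an interval for a mean is formed. Section 1.4.2 keeps all planned analyses "except when the number of patients in a subgroup of interest is below 5", a rule that counts patients and not patients with a cost.

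**The concern.** A Gamma distribution has support on values above 0. The SAP itself makes zeros foreseeable. Patients are 50 or older with an open top age class, and section 5.2.2.2.3 presents sick leave separately for patients in work, so non-workers are expected. Their indirect cost is 0. The interval costs leave out the inclusion visit, and sections 5.1.4.1.3 and 5.1.4.1.4 report no emergency visit or hospital stay. A patient with no visit, drug or sick leave in an interval therefore costs 0.

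The analyst must then improvise on a component of the primary objective. One route keeps the zeros in a quasi-likelihood fit and returns the ordinary mean. Another loses the zero-cost patients and returns the mean among users only, which is a different quantity from the mean over the population that section 5.2.2.3 defines. A reader of the results could not tell which was done. In a subgroup where nobody has sick leave, the log-link model has no finite estimate at all.

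**Working it through.** **The plan's own figures.**
- Daily allowance: 6.4×10⁹ / 204×10⁶ = 31.37 euro; 31.37 × 1.0438 = 32.74 euro. Reproduced.
- Precision at n = 100 (Table 2), 1.96 × SD/√n: 1.96 × 0.25/10 = 4.9% up to 1.96 × 2/10 = 39.2%. Reproduced.

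**Which costs are always positive.** Section 5.1.4.1.2 states: "The cost of the inclusion visit is evaluated according to the specialty of the investigator". The lowest tariff for an investigator's specialty is 23.00 euro. The payer part is 0.70 × 23 − 1 = 15.10 euro. Total, direct and medical-visit costs cumulated from inclusion are therefore at least 23.00 euro (societal) or 15.10 euro (payer), and the Gamma model is valid for them.

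**Which are not.** Indirect cost = days × 32.74, which is 0 when days = 0. With any zero in the data, the Gamma log-likelihood is −∞ (shape 1.5) or +∞ (shape 0.5).

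**Size, if zeros are lost.** Let p be the share of patients with sick leave. All-patient mean = p × (mean among users), so a fit to positive values overstates it by 1/p. The SAP does not give p. Assumed: n = 100, users average 10 days (327.40 euro), relative SD among users about 1 (lognormal quantiles). Both fits are intercept-only Gamma/log with Pearson scale; the interval is mean × exp(±1.96 × CV/√n), with CV and n taken from the patients in the fit.

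| p | Zeros kept: mean (95% CI), euro | Positives only: mean (95% CI), euro | Ratio |
|---|---|---|---|
| 10% | 32.74 (15.18-70.60) | 327.40 (195.59-548.05) | 10 |
| 20% | 65.48 (38.01-112.81) | 327.40 (223.24-480.15) | 5 |
| 30% | 98.22 (63.47-152.00) | 327.40 (237.68-451.00) | 3.33 |

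For p = 10% with zeros kept, CV = 3.92, and 32.74 × exp(±1.96 × 3.92/10) gives 15.18 to 70.60. In no row do the two intervals overlap.

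**Coverage of the all-patient mean** by nominal 95% intervals, simulated under the same assumptions (3,000 runs, 999 bootstrap samples), for p = 10/20/30%:

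| n | Positives only | Zeros kept, Pearson scale | BCa bootstrap |
|---|---|---|---|
| 100 | 0/0/0% | 91.6/92.2/93.2% | 90.7/91.4/92.4% |
| 50 | – | 90.3/91.6/93.2% | 88.4/90.2/91.5% |
| 16 | – | 74.8/87.2/90.6% | 72.4/83.4/87.6% |

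n = 16 is the SAP's 16% PHN hypothesis applied to 100 patients. Runs with no user count as not covered.

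**All-zero subgroup.** P(no user) = (1 − p)ⁿ. For the class aged 70 or over, with size and p both assumed, p = 1/2/5% gives:
- 30 patients: 74/55/22%
- 40 patients: 67/45/13%
- 50 patients: 61/36/8%

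**The case against.** The strongest reply is about scope. The model sentence comes straight after the sums from inclusion, and on that nearest reading it covers only costs that are always positive, so nothing is wrong with the model itself. This stands for total and direct costs. It does not settle indirect cost, which the primary objective names alongside direct cost, nor the interval costs. Section 5.2.2.2 says that all section 5.1 variables are analysed in both cohorts, and section 4 promises intervals for them.

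A second reply is that a default exists: sections 1.3.1 and 1.4.2 print ±1.96 × SD/√n for the mean of a continuous variable, and section 1.3.1 names costs as an example. That formula tolerates zeros, but it is given as a precision calculation and not as the analysis method. Under the assumptions above it covers about 87, 90 and 91% at n = 100, slightly less than the zeros-kept fit.

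A third reply limits the harm, and it stands. A reader might infer that the trial's indirect costs will be overstated 3 to 10 times. The SAP does not support that. It nowhere says that zero-cost patients are dropped; dropping them would contradict the population in section 5.2.2.3; and the required counts, histograms and sick-leave summaries would help to expose it. Section 8 names SAS 9.4 but no procedure, so the document does not settle what would happen.

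**Conclusion.** The plan is wrong as written for indirect cost and for interval costs. The only estimation method that it assigns to cost means has a likelihood undefined at 0, and neither its scope nor the handling of zeros is stated. On the narrow reading of scope, these costs have no prescribed interval method instead. Total, direct and medical-visit costs from inclusion are unaffected, so it would be wrong to conclude that the cost analysis as a whole is invalid.

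If, and only if, zeros fall out of the fit, the mean is inflated by 1/p. That factor is exact, but 3.3 to 10 depends on an assumed p of 30% to 10%; the coverage figures also assume the distribution of days among users. With zeros kept, the point estimate is the correct arithmetic mean. Severity is minor to moderate: the study is descriptive, but a component of its primary objective is involved.

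**What to change.** In section 5.2.2.3:
1. Keep the Gamma/log model for costs that are strictly positive: total, direct and medical-visit costs cumulated from inclusion.
2. For indirect cost, and any other component or interval cost that can be 0, estimate the arithmetic mean over all patients with the required interviews, zeros included. Name an interval method that tolerates zeros. A log-link quasi-likelihood fit with Pearson scale is preferable (about 92-93% coverage at n = 100 under the assumptions). A bootstrap interval is an acceptable alternative, though BCa covered less in all nine settings tried.
3. Report the number and percentage of patients with a cost above 0.
4. Where every value is 0, report 0 without a model.
5. Check that mean indirect cost equals mean sick-leave days × 32.74 in the same patients.

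The cost is a few sentences, a few lines of code and a little extra analysis; no new data are needed. The change settles what is estimated but does not cure small samples: at about 16 PHN patients, intervals for costs with many zeros remain unreliable by either method.
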